2.2 Objectives

- a) To determine the clinical effectiveness of intravenous ferric carboxymaltose versus oral ferrous sulphate in postpartum women with moderate to severe iron deficiency anemia by conducting a randomized trial.
- b) To determine the incidence of adverse drug events including the incidence of hypophosphatemia in the mother and adherence with the use of intravenous ferric carboxymaltose and oral ferrous sulphate for treatment of postpartum anemia. We will evaluate biomarkers of calcium and phosphate homeostasis and bone turnover and measure vitamin D, alkaline phosphatase, procollagen type 1 N-terminal propeptide (P1NP), fibroblast growth factor 23 (FGF23), calcium and Phosphate levels.
- c) To evaluate the acceptability and feasibility of using intravenous ferric carboxymaltose in treating postpartum anemia in Nigeria by conducting an alongside implementation study.

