3.1.2 Secondary outcomes

- a) Proportion of women with postpartum depression, measured using the Edinburgh Postnatal Depression Scale at six weeks and six months postpartum.
- b) Change in mean postpartum hemoglobin levels at two weeks and six weeks postpartum.
- c) Achievement of a non-anemic state (Hb≥11.0g/dl) at six months postpartum.
- d) Prevalence of moderate/severe anemia at six weeks and six months postpartum. Moderate anemia is defined as hemoglobin level 7.0-9.9g/dl and severe anemia as hemoglobin level <7.0g/dl.
- e) Change in mean serum ferritin, serum transferrin, serum iron and % transferrin saturation at two weeks and six weeks postpartum.
- f) Need for blood transfusion after iron treatment during the first 6 weeks postpartum.
- g) Prevalence of fatigue at six weeks and six months postpartum, measured using the Fatigue Severity Scale (revised FSS-5R version) (22).
- h) Proportion of women with secondary postpartum hemorrhage after treatment. This will be defined as excessive bleeding requiring surgical intervention or blood transfusion from 24 hours after delivery till 12 weeks postpartum (23).
- i) Proportion of infants being breastfed (exclusive and any) at six weeks and six months postpartum.
- j) Prevalence of impaired maternal-infant bonding at six weeks and six months postpartum measured using the Mother-to-Infant Bonding Scale (MIBS) (20).
- k) Incidence confirmed or suspected maternal infection within 6 weeks of birth, as defined by a new prescription of antibiotics for presumed perineal wound-related infection, endometritis or uterine infection, urinary tract infection or other systemic infection (clinical sepsis).
- I) Incidence of hypophosphatemia at two weeks and six weeks postpartum. We will measure vitamin D, alkaline phosphatase, P1NP, FGF23, Ca, PO₄, which are biomarkers of phosphorus homeostasis and bone turnover. Hypophosphatemia is defined as serum phosphate level <2.5mg/dL (0.81mmol/L). Mild hypophosphatemia as 2-2.5 mg/dL (0.65-0.81 mmol/L), moderate as 1-2 mg/dL (0.32-0.65 mmol/L), and severe as <1 mg/dL (0.32 mmol/L).
- m) Incidence of early neonatal death, defined as death of newborn from enrolment of the mother to before seven completed days.
- n) Incidence of late neonatal death, defined as death of the newborn from enrolment of the mother to before 28 completed days.
- o) Incidence of infant death, defined as death from enrolment before the age of six months.

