4.9 Laboratory evaluations

Standard clinical laboratory evaluations will be performed as follows:

- Hemoglobin concentration with the Hemocue haemoglobinometer at screening, two and six weeks and six months postpartum. Complete the *Hb check worksheet* as appropriate (*Appendix i*).
- Malaria rapid diagnostic test (RDT) with SD BIOLINE Malaria Ag P.f at enrollment, two and six weeks
 postpartum and if symptomatic for malaria at any time. Complete the *Malaria POCT worksheet* as
 appropriate (Appendix ii).
- Full blood count at baseline (enrollment), two weeks, six weeks, and six months postpartum. At each visit, 4mls of blood will be collected in an EDTA vacutainer. *Complete blood sample collection log for study visits on REDCap (Appendix iii)*.
- Iron profile: comprises serum iron, serum ferritin, serum transferrin and percentage transferrin saturation will be done at baseline (enrollment), six weeks and six months postpartum. At each visit, 4mls of blood will be collected into a Serum separating tubes (SST) tube. *Complete blood sample collection log for study visits on REDCap*
- Maternal serum phosphate and other biomarkers: The biomarkers of phosphate homeostasis and bone turnover to be measured are Vitamin D, alkaline phosphatase, total procollagen type 1 N-terminal propeptide (P1NP), fibroblast growth factor 23 (FGF23), calcium (Ca) and phosphate (PO4) at baseline (enrollment), 2 weeks (Ca, PO4 and ALP only) and at 6 weeks postpartum. Two (2) SST tubes will be used for sample collection and 4mls of blood will be collected in each tube.
 Complete blood sample collection log for study visits on REDCap.

All samples aside the point of care tests (POCT) will be analyzed at Synlab (an internationally accredited medical laboratory). As a third-party, a contract is in place between the University of Lagos and Synlab. The following steps will be taken at blood sampling:

- Research nurse assistants will collect blood sample as indicated for study visit using an appropriate vacutainer system.
- Complete the *laboratory tests request form* (Appendix iv) with participant's study ID, study site code and visit type (PP-1 to PP-4) to accompany the samples to the lab.
- Document date and time samples were taken and type of test in blood sample collection log on REDCap for study visit.
- Call the dispatch rider for samples pick up within 2-3 hours of sample collection.

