7.4 Data analysis plan for adverse events (Harm)

Using intention to treat analysis, the absolute risk, the frequency/incident rate and severity grade of anticipated adverse drug reactions such as abdominal pain, nausea and vomiting, hypotension and hypophosphatemia for participants in each study arm, the incident rate of any Serious Adverse Reactions (SAR) which are SAEs that are thought to be causally linked to the trial drug and Suspected Unexpected Serious Adverse Reaction (SUSAR) which are unexpected occurrence of a SAR for each arm of the study will be collated and analyzed. The mean and SDs or median and interquartile range for serum phosphate level will be calculated as appropriate, while extreme values will be stated if observed.

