9.4 Data analysis plan

Primary analysis will be conducted by the intention to treat principle. Categorical variables will be expressed as frequencies and percentages. For continuous variables, a Shapiro-Wilk test of normality will be performed, and normally distributed data will be presented as means ± SD, while non-normally distributed data will be presented as median and interquartile range (IQR). However, the literature will be reviewed to ensure that variables are handled in their natural form. The effect of IV iron (vs. oral iron) on the primary endpoint (anemia at six weeks post-partum) would be analyzed using log-binomial regression models to obtain relative risks, 95% confidence intervals and p-values. The extent to which inclusion of baseline covariates modifies the precision of estimates would be explored. Generalized linear mixed models will be used to estimate the effect of treatment arm on repeated measures of hemoglobin and iron status biomarkers. The proportions of participants in the treatment arms who are anemic or iron deficient, and the proportions of participants who achieve anemia correction at 6 weeks and 6 months follow-up with be compared. Kaplan Meir plots and log-rank test will be used to explore the time to anemia correction. Subgroup analysis will be conducted to compare study findings by mode of delivery (caesarean vs vaginal delivery), and by the occurrence of primary post-partum hemorrhage. Two tailed test of hypothesis and 95% confidence interval is assumed as statistical level of significance. Stata version 17 (Stata Corp, Texas, USA) statistical software will be utilized for analysis. The variance estimator with cluster option (clustering on site of study) will be utilized.

Interim analysis will be conducted after achieving half of the sample size. Based on O'Brien-Fleming method (29), the threshold for significance of the primary endpoint at the interim analysis will be alpha = 0.0054. The clinical trial is terminated if the null hypothesis is rejected. The alpha level for the analysis at the end of the study will be adjusted to 0.0492 based on alpha adjustment based on O'Brien-Fleming method.

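### The continuous serum phosphate level is assigned only descriptive summaries, while the protocol's repeated-measures treatment-effect model names hemoglobin and iron markers alone

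*Protocol*

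**What the plan says.** - **Objective.** Protocol 2.2(b) covers the incidence of hypophosphatemia and also the underlying markers: "We will evaluate biomarkers of calcium and phosphate homeostasis and bone turnover and measure vitamin D, alkaline phosphatase", with P1NP, FGF23, calcium and phosphate completing the list.
- **Outcome.** In 3.1.2, outcome (l) is headed "Incidence of hypophosphatemia at two weeks and six weeks postpartum". The six markers are listed there as measured, and a cut-off is given for phosphate only.
- **Sampling.** Section 4.9 schedules the markers "at baseline (enrollment), 2 weeks (Ca, PO4 and ALP only) and at 6 weeks postpartum". Phosphate, Ca and ALP therefore have an enrolment value and two follow-up values; vitamin D, P1NP and FGF23 have an enrolment value and one follow-up value.
- **Harms analysis (7.4).** By intention to treat and for each arm, it plans "the absolute risk, the frequency/incident rate and severity grade of anticipated adverse drug reactions such as abdominal pain, nausea and vomiting, hypotension and hypophosphatemia". For the phosphate level it then says: "The mean and SDs or median and interquartile range for serum phosphate level will be calculated as appropriate", and that extreme values will be stated if seen.
- **Efficacy analysis (9.4).** "Generalized linear mixed models will be used to estimate the effect of treatment arm on repeated measures of hemoglobin and iron status biomarkers". On baseline values it says: "The extent to which inclusion of baseline covariates modifies the precision of estimates would be explored"; that sentence directly follows the primary-endpoint model.

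**The concern.** Two sections of the same protocol handle similar data differently. Iron markers, taken at enrolment, 6 weeks and 6 months, get a model whose purpose is to estimate the effect of treatment arm. The phosphate level, taken at enrolment, 2 and 6 weeks, gets summary statistics. An analyst who follows both sections literally would report a treatment effect for ferritin and only a description of phosphate.

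This matters because the protocol itself raises the phosphate question. Its background (1.1) notes that ferric carboxymaltose has been found to lower serum phosphate, and 2.2(b) makes phosphate homeostasis an object of evaluation. A specified mean difference at each visit, with its confidence interval, answers that more directly than two sets of summaries. Fixing the method beforehand also removes the later choice between comparing follow-up values, changes from enrolment, or adjusted values, on a safety question in an open-label trial.

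**Working it through.** **1. Text check.** The protocol states no SD, effect size or power for phosphate, so there is no figure of its own to reproduce. Set side by side:

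| Measure | Values per woman | Stated analysis |
|---|---|---|
| Hemoglobin, iron markers | repeated | mixed model, effect of arm (9.4) |
| Hypophosphatemia (yes/no, grade) | 2 and 6 weeks | risk, incidence and severity by arm, ITT (7.4) |
| Phosphate level | enrolment, 2, 6 weeks | descriptive summaries and extremes (7.4) |
| Ca, ALP | enrolment, 2, 6 weeks | none stated |
| Vitamin D, P1NP, FGF23 | enrolment, 6 weeks | none stated |

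Only the phosphate-level row shows a method that is both stated and weaker than the one used for comparable data. The last two rows are silence.

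**2. Size of the precision part (illustration).**

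Inputs from the protocol (4.3): 700 women per arm and 10% loss to follow-up, so n = 700 × 0.90 = 630 per arm. From 9.4: two-sided tests and 95% intervals.

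Assumptions: every retained woman has a phosphate value, the SD is equal in both arms, clustering by site is ignored, and the correlation r between enrolment and follow-up values lies between 0.2 and 0.7. The protocol does not give r. Enrolment blood is drawn 6 to 48 hours after delivery, so a low r is plausible and the range starts low.

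Formulas, in SD units:
- Follow-up values only: SE = √(2/n) = √(2/630) = 0.0563.
- Enrolment value as covariate: SE = √(2(1 − r²)/n).
- Narrowing of the interval: 1 − √(1 − r²).
- Difference detectable with 90% power: (1.960 + 1.282) × SE.

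| r | SE adjusted | Interval narrower by | Detectable difference |
|---|---|---|---|
| unadjusted | 0.0563 | – | 0.183 SD |
| 0.2 | 0.0552 | 2.0% | 0.179 SD |
| 0.5 | 0.0488 | 13.4% | 0.158 SD |
| 0.6 | 0.0451 | 20.0% | 0.146 SD |
| 0.7 | 0.0402 | 28.6% | 0.130 SD |

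**3. Reading.** Even without adjustment the trial could detect about 0.18 SD with 90% power. Adjustment gives a gain that ranges from negligible to useful, depending on an unknown r. The main gap is that no between-arm estimate is specified for the level; precision comes second.

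**The case against.** The strongest case against is that this is detail for an SAP, which may exist and is not at hand. Section 7.4 says that summaries will be calculated; it does not say that nothing else will be done. Section 9.4 likewise promises descriptive statistics for continuous variables in general and then adds models, so in this protocol a descriptive sentence does not exclude a model. It also sets two-tailed tests and 95% confidence intervals as the general standard. And the headline of outcome (l) is an incidence, for which 7.4 has a plan.

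Much of this stands, and it rules out several stronger readings that a reader might infer:

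- *The phosphate safety question has no analysis.* Not supported: risk, incidence and severity of hypophosphatemia are planned by arm.
- *The protocol forbids or excludes an effect estimate for the level.* Not supported: it assigns none, which is different.
- *An unadjusted comparison would mislead.* Not supported: under randomization it is unbiased, and chance imbalance at enrolment is already reflected in its standard error.
- *The lack of a method for vitamin D, ALP, P1NP, FGF23 and Ca is an error.* Not supported: the protocol is silent, and such detail is commonly left to the SAP.

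What the objection does not remove is the phosphate level itself. There the protocol is not silent: it states a method, and that method is weaker than the one it gives to hemoglobin and iron markers.

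**Conclusion.** The point holds in a limited form. For the continuous phosphate level, 7.4 states descriptive summaries only, and the treatment-effect model of 9.4 is written for hemoglobin and iron markers, although phosphate has the repeated values and enrolment measurement that such a model needs. The binary outcome is not affected, nor is the primary result.

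The cost is an unspecified between-arm estimate plus some lost precision: an interval about 2% wider than necessary to be removed at r=0.2, about 13% at r=0.5 and about 20% at r=0.6, expressed as narrowing relative to the unadjusted interval. These percentages rest entirely on the assumed r; the standard errors also rest on 630 evaluable women per arm and on ignoring site clustering. It is a low-cost improvement worth making, not a flaw that prevents the arms from being compared.

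**What to change.** - **Section 7.4:** keep the phosphate summaries and extreme values, labelled as descriptive support, and refer to 9.4 for the comparison between arms.
- **Section 9.4:** extend the mixed-model sentence to serum phosphate, together with Ca and ALP, which share its schedule. State the terms: arm, visit, arm-by-visit and the enrolment value, with site handled as elsewhere in 9.4. Report the mean difference between arms with a 95% confidence interval at 2 and at 6 weeks. The enrolment term has to be written out, because adding marker names alone would not bring in the adjustment.
- **SAP:** confirm that the markers with no stated analysis are covered. Vitamin D, P1NP and FGF23 at 6 weeks can be handled by regression on arm and enrolment value.

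The cost is a few lines of text and a few model runs on data already being collected. No extra samples, visits or participants are needed.

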7.5 Validation of the Patient Reporting Outcome (PRO) Tool

7.5.1 Objective

To evaluate the test-retest reliability of the Edinburgh Postnatal Depression Scale (EPDS), Modified 5-item Fatigue Severity Scale (FSS-5R), Mother to Infant Bonding (MIB), and WHO quality of life brief version (QOL-BREF) in Nigerian languages among participants in the IVON-PP trial.

7.5.2 Study population

A sample of women with an upcoming six-week visit will be selected for the sub-study. Consent into the validation sub-study will take place at enrolment into IVON-PP trial or at the two weeks' visit. All women enrolled in the study in November 2023 and onwards will be considered for inclusion in the validation sub-study.

To be eligible for the sub-study, participants must be:

- 1) Eligible for and enrolled in the IVON-PP trial.
- 2) Willing to attend one extra visit around the time of the six weeks' visit.

Participants' health status or randomization arm will not, otherwise, be a basis for inclusion or exclusion. Participants' informed verbal consent will be sought.

7.5.3 Study design

Participants will be invited to attend an extra postpartum visit, one to four weeks before or after their scheduled 6 weeks' postpartum visit, at the participants' convenience. The study team will follow the regular study visit schedule (2 weeks and 6 weeks post-partum) to the extent possible, and schedule additional visits as necessary.

All consecutive study participants will be invited to participate until the minimum sample size for the chosen language is reached.

To the extent possible, the extra visit will be conducted in the same manner as the scheduled six weeks' visit. That is, if the scheduled six weeks' visit occurs as a physical in- hospital or at the participant's home, then the extra visit will take place at the same site as the study schedule visit. The same will apply for visits completed virtually.

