4.10.3 Follow-up visits (2, 6, and 12 weeks postpartum)

• Each participant will have follow-up visits at home or healthcare facility whichever is preferred except the 6 weeks visit which as routine should be at the health care facility.

The following steps will be taken at the follow up visits:

- 1. Go to REDCap, using the participant's study ID-
 - Complete and submit the Edinburgh Postnatal Depression Scale (EPDS) e-form (Appendix xi) at 6 weeks visit.
 - Complete and submit the Maternal infant bonding scale e-form (Appendix xii) at 6 weeks visit.
 - Complete and submit the fatigue scale e-form (Appendix xiii) at 6-week visit.
 - Complete and submit the quality of life (WHOQOL BREF) scale e-forms (Appendix xiv) at 6 weeks visit.
 - Evaluate for the presence of any symptom and sign (adverse event(s) AEs)) and if any,
 complete and submit the adverse event e-form for all follow up visit.

The visit e-CRF will be available to you ONLY after completing and submitting the above steps on REDCap.

- Evaluate compliance to study drug and document in the e-CRF.
- Complete follow-up visits e-CRF (Appendix xv) and relevant source documents
- Re- supply study drug (control arm) in an amount sufficient to last until the next follow up visit up to the 6th week visit.
- Counsel and necessary referral (e.g., family planning clinic, psychosocial support etc.).

2. Additional steps

- Perform malaria rapid diagnostic test (RDT) with SD BIOLINE Malaria Ag P.f and complete the *Malaria POCT worksheet* as appropriate (2- and 6-week postpartum visits).
- Do hemoglobin concentration check with the haemoglobinometer at every follow up visit. And complete Hb check worksheet as appropriate.
- Take blood samples for laboratory tests as indicated for visit type and complete the blood sample collection log on REDCap. This sample can also be used for the hemoglobin concentration check.
- Counsel as appropriate based on any queries they might have about their health or that of their newborn/baby.

The research team at site will be responsible for the visits and attending to the participant and resupplying the participants with the study drugs at two weeks.

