7.5.5 Data collection

Data will be collected electronically using REDCap. Surveys will not be anonymous as it will be necessary to link the two visits for each participant.

The preferred language selected by the participant for the main study will be the preferred language for this sub-study. All participants will complete the instrument in the same preferred language on the date of the 6 weeks' visit, as well as at an extra study visit.

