7.5.7 Sample size

The sample size required was determined to be 118 per language based on a median of the sample sizes that have worked well for previous studies among patients (40). For the EPDS, the sample size for some published translation and validation studies have been 87(41), 100(42), 118(43), 123(44), and 451(45). For the MIB, sample sizes that have worked well include 63(46) and 554(47). For the FSS, the sample size for published translation and validation studies have included 23(48), 83(49), 113(50), 123(51), and 427(52). For the WHOQOL-BREF, sample sizes that have worked well include 228(53) and 538(44).

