- XVIII. Drug Accountability Form (FCM, FS, ANTI-MALARIA)
- XIX. NCI Common Terminology Criteria for Adverse Events version 5 (Abridged)
- XX. SAE report form
- XXI. NAFDAC Pharmacovigilance form
- XXII. Pre-trial site assessment and selection visit
- XXIII. Study initiation checklist
- XXIV. Site monitoring visit checklist
- XXV. Protocol deviation/ violation form.
- XXVI. Site monitoring visit log
- XXVII. Referral for psychiatric consultation

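### The validation sub-study may give the four scales before the six-week visit, so the six-week scale outcomes would be a repeat measurement for some women and a first one for others

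*Protocol*

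**What the plan says.** Section 7.5 of the protocol describes a test-retest sub-study of the EPDS, FSS-5R, MIB and WHOQOL-BREF among trial participants.

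- **Timing (7.5.3).** The extra visit takes place "one to four weeks before or after their scheduled 6 weeks" postpartum visit, "at the participants' convenience". The section adds: "The study team will follow the regular study visit schedule (2 weeks and 6 weeks post-partum) to the extent possible".
- **Instruments (7.5.4, 7.5.5).** All four scales are completed at both the six-week visit and the extra visit, in the same language.
- **Size (7.5.7).** "The sample size required was determined to be 118 per language". Section 7.5.3 calls this a minimum, and invitations continue until it is reached.
- **Who takes part (7.5.2).** Women with a six-week visit still to come, enrolled from November 2023 on, who are willing to attend one extra visit. Arm plays no part in selection.
- **Main trial.** Sections 4.10.3 and 4.10.5 and Table 3 give the scales at six weeks and six months only. Secondary outcome (a) is depression, "measured using the Edinburgh Postnatal Depression Scale at six weeks and six months postpartum". Fatigue (g), bonding (j) and quality of life (r) are also assessed at six weeks. Outcome (r) in section 3.1.2 lists an enrollment measure as well, but Table 3 shows none.
- **Referral.** Section 4.10.3 includes, at follow-up visits, "Counsel and necessary referral (e.g., family planning clinic, psychosocial support etc". The appendix list contains a form titled "Referral for psychiatric consultation".

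**The concern.** A reliability sub-study should not change how the parent trial's outcomes are measured. Here it can. If the extra visit comes first, the six-week score recorded as a trial outcome is a second completion within four weeks. Whether that happens depends on the woman's language, when she enrolled and which date suits her. The six-week outcomes then combine two kinds of measurement, and section 7.5 neither fixes the order nor addresses the effect on the trial outcome.

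For depression there is a further possibility. A high score at an early extra visit could lead to counselling or referral before the trial's own assessment, so that some cases are no longer cases at six weeks. For the other three scales the issue is only that the questions have been answered before.

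**Working it through.** **1. When can the extra visit fall?** Before: 6 − 4 = week 2 to 6 − 1 = week 5. After: 6 + 1 = week 7 to 6 + 4 = week 10. The scheduled two-week visit lies exactly at the early limit, and section 7.5.3 names it as part of the schedule to follow where possible. An early extra visit is thus an expected route.

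**2. First or second completion?**

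| Extra visit | First completion | Trial's six-week score is |
|---|---|---|
| Early (weeks 2–5) | extra visit | the second completion |
| Late (weeks 7–10) | six-week visit | the first completion |
| Not in sub-study | six-week visit | the first completion |

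This is clear for outcomes (a), (g) and (j). It holds for (r) only if the enrollment measure in section 3.1.2 is not taken, as Table 3 suggests.

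**3. The plan's figure of 118.** Section 7.5.7 bases it on a median of earlier sample sizes. The EPDS sizes listed are 87, 100, 118, 123 and 451, with median 118. The figure reproduces. (All 14 listed sizes pooled have median 120.5.)

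**4. Share of women affected.** Maximum share = 118 × number of languages ÷ 1,400, if every extra visit is early. The number of languages is not stated, so it is varied:

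- Three (Yoruba, Hausa and Igbo, the translations named for consent in 4.10.1)
- Four (adding English)
- Five (adding Pidgin English, named for the focus groups in 8.3.1.1)

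| Languages | Women | All early | Half early |
|---|---|---|---|
| 3 | 354 | 354/1,400 = 25.3% | 12.6% |
| 4 | 472 | 472/1,400 = 33.7% | 16.9% |
| 5 | 590 | 590/1,400 = 42.1% | 21.1% |

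Against the 1,400 × 0.90 = 1,260 women expected after the planned 10% loss, the all-early shares are 28.1%, 37.5% and 46.8%.

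**5. Effect on the depression comparison, if early referral works.** Let s be the share seen early and r the share of their cases resolved before six weeks, both equal in the two arms. Each arm's risk is multiplied by (1 − s·r).

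- Risk difference: (1 − s·r)(p₁ − p₀), smaller by the fraction s·r.
- Relative risk: p₁(1 − s·r) ÷ [p₀(1 − s·r)] = p₁/p₀, unchanged.

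The protocol gives no value for r. It can range from 0 (no shrinkage) to 1 (shrinkage of s). As an illustration only, r = 1/3 with four languages gives 0.169 × 0.333 = 5.6% (half early) or 0.337 × 0.333 = 11.2% (all early).

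**The case against.** The strongest reply is that none of this biases the comparison of arms. Section 7.5.2 makes selection independent of arm, and section 4.5 has these scales collected by a nurse blinded to allocation. If the effect is equal in both arms, the relative risk does not move. Relative risk is the only effect measure that section 9.4 names for a binary endpoint (for the primary; none is named for depression). This stands. A reader might infer that the depression effect is pulled towards zero; that holds for the absolute difference only, and only if early cases resolve.

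A reader might also infer that women will be referred after an early high score. The protocol does not say so. Section 7.5 is silent on scoring and referral at the extra visit, no EPDS cut-off is given, and the psychiatric referral form appears only as an appendix title. Section 4.10.3 already allows referral at the two-week visit without the sub-study, so an early scale could at most add to an existing pathway.

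Nor is a fixed fraction of women, such as one third, supported. It needs exactly four languages, each reaching 118 among women enrolled from November 2023, with every extra visit early. Because 118 is called a minimum, one third is not a strict ceiling either.

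Finally, it can be said that handling of these women belongs in the statistical analysis plan. The analysis may, but the order of visits is set in section 7.5.3, and no later analysis can turn a second completion into a first.

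**Conclusion.** The point holds as a minor design weakness. As written, section 7.5.3 lets an optional sub-study turn the six-week outcomes (a), (g) and (j) into a repeat measurement for some women and leave them a first one for others. The same applies to (r) if no enrollment measure is taken.

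The share affected is at most about 25% to 42% of 1,400 for three to five languages, and about 13% to 21% if half the extra visits are early. These figures assume that each language reaches 118 and no more. The true share could be lower if a language falls short.

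The expected consequence is a mixed measurement. For depression there may also be fewer events or a smaller absolute difference, with the relative risk about unchanged if the effect is equal in both arms. The documents do not support a claim of bias towards either arm. The primary hemoglobin outcome is not affected.

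**What to change.** In section 7.5.3, delete *before or* and remove the two-week visit as a possible retest. State that the extra visit takes place only after the six-week scales have been completed, at a short interval, for example one to two weeks. No woman's six-week score is then a sub-study repeat.

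For women already seen early, record the order of the two visits and run a sensitivity analysis of the six-week scale outcomes without them. Visit order is decided after randomization, so that analysis is supportive only.

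**Cost.** The text change is small. The two-week visit can no longer serve as the extra visit, so each sub-study woman needs a separate one, with transport reimbursed under section 7.5.6; section 7.5.2 already requires willingness to attend one. Some retests may follow further anemia treatment (note b to Table 2) or referral begun at six weeks, which could add true change between the two scores. The short interval limits this.
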